Renal findings	
 • Kidney: hyaline droplets in proximal tubules, weight increase in both species 
 • Hyaline droplets associates with absorption and secretion of the cephem antibiotics in lysosome • No degenerative changes • Probably mixture of drug and protein (stimulation of lysosomal turnover) • Accompanied by increases in urinary N-acetyl-β-D-glucosaminidase (exploratory biomarker of lysosomal enzyme) at all doses and slight change in urinary albumin at 2000 mg/kg (relevance unclear) 	
 • Inclusion/Exclusion 
 • Healthy subjects • Serum creatinine greater than the upper limit of normal (ULN) • Estimated glomerular filtration rate (eGFR) <90 mL/min/1.73 m² as calculated by the Chronic Kidney Disease Epidemiology Collaboration formula • Albumin to creatinine ratio (ACR) ≥0.03 mg/mg • Urinalysis negative for blood/protein • Monitor: 
 • Serum blood urea nitrogen, creatinine, eGFR, electrolytes, urinalysis • ACR during the study • Criteria to pause Part 1 progression or interrupt Part 2 dosing 
 • Creatinine change >0.3 mg/dL without alternative cause • New blood in urinalysis confirmed by microscopy without alternative cause • ACR ≥0.03 mg/mg
Injection site reactions	
 • Local irritation 
 • Gross: discoloration, hardening, wound, thrombosis • Histology: ulcer, perivascular/vascular inflammation, thrombus (1000/2000 mg/kg/day; rats and monkeys) • Considered due to high osmolality of the dosing formulations 	
 • Reduced osmolality preparation • Monitor injection site including proximal limb for vascular change

Potential Risk of Clinical Significance	Summary of Data/Rationale for Risk	Mitigation Strategy

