Serotonin (5-HT)-3 in vitro binding assay	
 • “Moderately” positive with 39% effect at 100 mmol (78 µg/mL) • High dose Cmax will reach similar concentration • No clear in vivo correlation from toxicology studies 
 • Possible BP effect in monkey cardiovascular study • Poor central nervous system penetration (approximately 3% blood) 	
 • Precautions c/w those indicated to mitigate the BP effect seen in monkey cardiovascular study • Enroll healthy subjects not on medications to avoid additive arrhythmogenic potential
Other		
Neurologic findings (seizures)	
 • Known risk (seizures) for some β-lactams and cephalosporins • Seen pre-clinically with lead compound • No adverse findings to 2000 mg/kg/ day × 4 weeks in rats or monkeys • Central nervous system administration study in rats negative 	
 • Specifically assess for negative history of seizures in past medical history at screening • Close monitoring during infusion in an acute care setting
Rash/Dermatologic toxicity	
 • Rash is a common adverse event (AE) of β-lactam antibiotics. Range of manifestations and severity from mild morbilliform drug eruption to hives, Erythema multiforme (EM), Stevens-Johnson syndrome (SJS) and toxic epidermal necrolysis (TEN) in rare cases 	
 • Exclude individuals with history of rash to penicillins or cephalosporins • Exclude individuals with history of EM/SJS/TEN to any medication • Close monitoring • Discontinuation criteria 
 • Any rash of Grade 3 or greater severity • Any rash characterized by: 
 • Hives • Concomitant fever or other symptoms suggesting systemic manifestations • Blistering • Ocular or genital involvement • Access to standard interventions (antihistamines, steroids if indicated, intensive care unit/burn unit care in worst case)
Anaphylaxis/hypersensitivity	
 • Common to all β-lactam antibiotics 
 • Approximately 10% cross reaction between cephalosporins and penicillins • Guinea pig immunotoxicity model negative 	
 • Conduct study in inpatient Phase I clinical unit • “Crash” cart availability • Exclude subjects with history of penicillin allergy

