5.4.3. Renal Stopping Criteria

Study treatment will be discontinued for a subject who meets any of the following criteria:

- Persistent (confirmed on recheck) elevation of serum creatinine (>0.3 mg/dL) without an alternative cause identified
- Albumin to creatinine ratio ≥ 0.03 mg/mg
- New blood in urinalysis confirmed by microscopy without an alternative cause identified

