5.4.7. Additional Safety Stopping Criteria

Individual subjects, dosed with GSK3342830 who have experienced the following should be considered for potential discontinuation in consultation with the GSK medical monitor:

- Any Grade 4 AE
- Grade 3 gastrointestinal AE (see [Appendix 6](#))
 - *If a subject has 3 or more unformed stools in a 24-hour time frame, see [Appendix 10](#) to determine if samples should be collected for *Clostridium difficile* testing.*
- Grade 3 renal or urinalysis finding (see [Appendix 6](#))
- Severe hypersensitivity
- Anaphylaxis (see [Appendix 7](#))
- Subjects with a systolic BP of <90 mm Hg or a change in systolic BP from baseline of 30 mm Hg with symptoms. Vital signs should be taken with the subject in a semi-supine position, having rested in this position for at least 5 minutes and findings are confirmed upon repeat measurements taken within 5 minutes with the subject in the same physical position.

Data will be reviewed by the investigator and sponsor for consideration of potential study stopping if:

- Two (2) or more subjects, within a dose level, receiving GSK3342830 experience a Grade 3 renal or urinary AE that is deemed possibly or probably related to study drug by the investigator.
- Two (2) or more subjects, within a dose level, receiving GSK3342830 experience Grade 3 hypersensitivity related AE that is deemed possibly or probably related to study drug by the investigator.
- Two (2) or more subjects, within a dose level, receiving GSK3342830 experience a Grade 3 AE of rash that is deemed possibly or probably related to study drug by the investigator.
- Two (2) or more subjects, within a dose level, receiving GSK3342830 experience a Grade 3 vital sign (heart rate or BP) abnormality that is considered an AE and is deemed possibly or probably related to study drug by the investigator. Vital signs should be taken with the subject in a semi-supine position, having rested in this position for at least 5 minutes and findings are confirmed upon repeat measurements taken within 5 minutes with the subject in the same physical position.
- One (1) or more subjects receiving GSK3342830 experience anaphylaxis that is deemed possibly or probably related to study drug by the investigator.

The grading for AEs is based on the US National Institute of Allergy and Infectious Diseases Division of Microbiology and Infectious Diseases (DMID) Adult Toxicity Table (see [Appendix 6](#)).

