6.3. Planned Dose Adjustments

- This protocol allows some alteration from the currently outlined dosing schedule. The maximum daily dose is planned to not exceed 6000 mg in Parts 1 and 3, and 4000 mg in Part 2.
- The decision to proceed to the next dose level of GSK3342830 will be made by the GSK study team and the investigator based on preliminary safety, tolerability, and PK data obtained in approximately 4 subjects for Part 1 and approximately 5 subjects for Part 2 that received active study treatment in the prior dose level. The actual doses to be administered may be adjusted based on the preliminary safety, tolerability, and PK data at previous dose levels; these dose adjustments may involve either an increase or a decrease in the planned dose. A schematic of the planned study design is presented in [Figure 3](#).

- The dosing schedule may also be adjusted to expand a dosing cohort to further evaluate safety and PK findings at a given dose level, or to add cohorts to evaluate additional dose levels. The study procedures for these additional subject(s) or cohort(s) will be the same as those described for other study subjects.
- If AEs, which are of severe intensity or greater and are consistent across subjects in a given dose level, or if unacceptable pharmacological effects, reasonably attributable in the opinion of the investigator to dosing with GSK3342830, are observed in 2 or more subjects in a dose level, further dose escalation will be temporarily halted and no further subject in subsequent cohorts will be dosed until a full safety review of the study has taken place. Relevant reporting and discussion with the medical monitor, relevant GSK personnel, and with the Ethics Committee will then take place before any resumption of dosing.
- If the same SAE occurs in more than 1 subject, further dose escalation will be temporarily halted and no further subject in subsequent cohorts will be dosed until a full safety review of the data has taken place.
- The previously mentioned criteria will apply even if measured PK parameters are below the PK stopping criteria, and every effort will be made to take a blood sample at the time of the event for PK analysis in the presence of any of the above events.

Figure 3 Planned Study Schematic

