Hyperbilirubinemia (when other liver function tests are in the normal range)	1.1 to <1.5 × ULN	1.5 to <2.0 × ULN	2.0 to 3.0 × ULN	>3.0 × ULN
Blood urea nitrogen	1.25 to 2.5 × ULN	2.6 to 5 × ULN	5.1 to 10 × ULN	>10 × ULN
Hyperuricemia (uric acid)	7.5 to 10.0 mg/dL	10.1 to 12.0 mg/dL	12.1 to 15.0 mg/dL	>15.0 mg/dL
Creatinine	1.1 to 1.5 × ULN	1.6 to 3.0 × ULN	3.1 to 6.0 × ULN	>6 × ULN or dialysis required
Rx = therapy, ULN = upper limit of normal.				

ENZYMES				
	Grade 1	Grade 2	Grade 3	Grade 4
Aspartate aminotransferase (AST)	1.1 to <2.0 × ULN	2.0 to <3.0 × ULN	3.0 to 8.0 × ULN	>8.0 × ULN
Alanine aminotransferase (ALT)	1.1 to <2.0 × ULN	2.0 to <3.0 × ULN	3.0 to 8.0 × ULN	>8.0 × ULN
Gamma glutamyl transferase (GGT)	1.1 to <2.0 × ULN	2.0 to <3.0 × ULN	3.0 to 8.0 × ULN	>8.0 × ULN
Alkaline Phosphatase	1.1 to <2.0 × ULN	2.0 to <3.0 × ULN	3.0 to 8.0 × ULN	>8.0 × ULN
Amylase	1.1 to 1.5 × ULN	1.6 to 2.0 × ULN	2.1 to 5.0 × ULN	>5.1 × ULN
Lipase	1.1 to 1.5 × ULN	1.6 to 2.0 × ULN	2.1 to 5.0 × ULN	>5.1 × ULN

ULN = upper limit of normal.

URINALYSIS				
	Grade 1	Grade 2	Grade 3	Grade 4
Proteinuria	1+ or 200 mg to 1 g loss/day	2 to 3+ or 1 to 2 g loss/day	4+ or 2 to 3.5 g loss/day	Nephrotic syndrome or >3.5 g loss/day
Hematuria	Microscopic only <10 RBC/hpf	Gross, no clots >10 RBC/hpf	Gross, with or without clots, or red blood cells casts	Obstructive or required transfusion

HPF = high powered field, RBC = red blood cells.

CARDIOVASCULAR				
	Grade 1	Grade 2	Grade 3	Grade 4
Cardiac rhythm	N/A	Asymptomatic, transient signs, no Rx required	Recurrent/persistent; symptomatic Rx required	Unstable dysrhythmia; hospitalization and treatment required
Hypertension	Transient increase >20 mm Hg; no treatment	Recurrent, chronic increase >20 mm Hg; treatment required	Acute treatment required; outpatient treatment or hospitalization possible	End organ damage or hospitalization required
Hypotension	Transient orthostatic hypotension with heart rate increased by <20 beats/minute or decreased by <10 mm Hg systolic BP. No treatment required	Symptoms due to orthostatic hypotension or BP decreased by <20 mm Hg systolic; correctable with oral fluid treatment	Requires IV fluids; no hospitalization required	Mean arterial pressure <60 mm Hg or end organ damage or shock; requires hospitalization and vasopressor treatment
Pericarditis	Minimal effusion	Mild/moderate asymptomatic effusion, no treatment	Symptomatic effusion; pain; EKG changes	Tamponade; pericardiocentesis or surgery required

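### The two-subject rash and vital-sign reviews in protocol 5.4.7 say Grade 3 without 'or higher', so read literally a Grade 4 event does not count (minor)

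*Protocol*

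**What the plan says.** Section 5.4.7 has two lists. The first concerns the individual subject. It names any Grade 4 AE, and separately some Grade 3 findings, as reasons to consider stopping that subject after consulting the medical monitor.

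The second concerns the study. Four of its bullets each need two or more subjects on active drug in one dose level, with an event the investigator considers possibly or probably related. The rash bullet covers subjects "receiving GSK3342830 experience a Grade 3 AE of rash that is deemed possibly or probably related to study drug by the investigator". The renal/urinary, hypersensitivity and heart rate/blood pressure bullets are also set at Grade 3, with nothing about worse grades. A fifth bullet calls the review after a single related anaphylaxis.

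Elsewhere the protocol includes the worse grades when it means to. In 4.6.1 a rash discontinuation criterion is "Any rash of Grade 3 or greater severity". In 6.3 the escalation rule begins "If AEs, which are of severe intensity or greater and are consistent across subjects in a given dose level".

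**The concern.** A safety threshold should not become harder to meet as events get worse. Under the literal wording, a second related rash at Grade 3 calls the review, but the same rash at Grade 4 does not.

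The grades are distinct categories in Appendix 6, and 5.4.7 itself lists Grade 4 apart from Grade 3 in its individual-subject list. Appendix 6 also tells the investigator to grade any clinical event judged serious or life-threatening as Grade 4, so a serious rash or blood pressure event leaves the Grade 3 count.

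These are named risks. Section 4.6.1 lists blood pressure and heart rate changes in monkeys, and rash up to Stevens-Johnson syndrome and toxic epidermal necrolysis. What is at stake is whether the study-level review is called without argument when it is most needed.

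**Working it through.** **The plan's own figures.** Section 9.2.1 gives the chance of at least one event among 6 active subjects:

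- True rate 5%: 1 − 0.95^6 = 0.265 (stated 26%).
- True rate 20%: 1 − 0.80^6 = 0.738 (stated 73%).

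Both reproduce closely. They say nothing about grade or about a two-subject rule, and 5.4.7 carries no stated operating characteristics.

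**The count.** Two affected subjects, each at Grade 3 or 4, give the pairings 3+3, 3+4 and 4+4. The literal text counts 1 of the 3; *Grade 3 or higher* counts all 3. This counts labels, not likelihoods.

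**Why no probability is claimed.** The documents give no rates by grade. With assumed per-subject rates p3 and p4 and n active subjects, the 5.4.7 count alone is met with probability P(X ≥ 2), where X is binomial(n, p3) under the literal text and binomial(n, p3 + p4) under the amended text. For n = 6 and p3 = 10%, the literal figure is 11.4%. The amended figure is 15.6% at p4 = 2% and 34.5% at p4 = 10%. The gap runs from about 4 to 23 percentage points purely on the assumed p4, and it ignores every other rule below.

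**What else catches 3+4 and 4+4 pairs.**

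- *Hypersensitivity.* Appendices 6 and 7 define the Grade 4 allergic reaction as anaphylaxis, and one related case already calls the 5.4.7 review. Almost nothing is left.
- *Renal/urinary.* Section 5.4.3 stops a subject on "Persistent (confirmed on recheck) elevation of serum creatinine (>0.3 mg/dL) without an alternative cause identified". Section 4.6.1 has a list headed "Criteria to pause Part 1 progression or interrupt Part 2 dosing" with similar thresholds. Grade 3 creatinine in Appendix 6 is 3.1 to 6.0 times the upper limit of normal, so these criteria act far earlier.
- *Rash and vital signs, 4+4.* Many Grade 4 definitions in these categories are SAEs in substance. Hypotension, for example, is "Mean arterial pressure <60 mm Hg or end organ damage or shock; requires hospitalization and vasopressor treatment". The same-SAE rule in 6.3 reads in part: "If the same SAE occurs in more than 1 subject, further dose escalation will be temporarily halted and no further subject in subsequent cohorts". Dosing there waits for a full safety review. That rule has no relatedness or dose-level condition.
- *Rash and vital signs, 3+4.* Both events are severe or worse. If they are attributable and consistent across subjects in the dose level, 6.3 halts escalation pending a full safety review.
- *Any pairing.* Section 6.4 escalates a safety signal found in subjects on drug, with no grade limit, and possible halting of dosing is among the actions. A single Grade 4 AE also brings in the medical monitor under 5.4.7.

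**What is left.**

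1. *Pairs that are neither consistent nor the same SAE.* A Grade 3 hypotension and a Grade 4 hypertension fall in one 5.4.7 category (blood pressure), but are arguably not consistent under 6.3 and are not the same SAE.
2. *Events in the current or last cohort.* The express halt in 6.3 names escalation and later cohorts. Its severity rule adds that discussion with the medical monitor, sponsor personnel and the "Ethics Committee will then take place before any resumption of dosing". That can be read to reach the current cohort but does not say so. After the 4000 mg TID cohort no later Part 2 cohort is planned. Appendix 9, Table 9 predicts a median AUC(0-24) of 3078 h•µg/mL there, against the NOAEL value of 2875.
3. *Low blood pressure.* The mandatory stops in 5.4.5 cover only high blood pressure and high heart rate. Low blood pressure appears in 5.4.7 only as a matter to consider for the individual.

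**The case against.** The strongest reply is that 6.3 already does more than 5.4.7. It requires a halt, a full safety review and discussion with the Ethics Committee, whereas 5.4.7 asks only for a review to consider stopping. Two related rashes, or two blood pressure events in the same direction, would ordinarily be called consistent. Most 4+4 pairs would meet the same-SAE rule. Section 6.4 adds a route with no grade threshold, 10.5 lets the sponsor suspend the study at any time for safety, and a sensible team would treat Grade 3 as a floor anyway.

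Most of this stands and sets the size of the point. It does not remove it. The 6.3 rules carry conditions that 5.4.7 does not (consistency, or the same SAE), and 6.4 depends on judgment within the dose-escalation review. The floor reading is also weakened by 5.4.7 naming Grade 4 separately a few lines earlier.

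Three stronger readings are tempting, and the documents support none of them:

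- *Grade 4 events escape study-level review.* They do not, given 6.3 and 6.4.
- *Grade 4 was left out by design.* No rationale for that appears anywhere; it looks like drafting.
- *The gap can be measured by the doses that Part 2 subjects would still receive after a second event.* The 5.4.7 review does not itself pause dosing, so amending its trigger would not by itself stop any infusion.

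**Conclusion.** The wording defect is real and its consequence is minor. It matters for rash and heart rate/blood pressure pairs graded 3+4 or 4+4 that fall between the 6.3 rules, or that occur where the express 6.3 halt has no later dosing to stop. The effect on the renal/urinary and hypersensitivity bullets is slight.

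The conclusion assumes that the bullets are applied as written and that events are graded by Appendix 6. If the team already reads Grade 3 as a minimum, the change only records existing practice.

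**What to change.** In each of the four two-subject bullets of 5.4.7, replace *Grade 3* with *Grade 3 or higher*, in line with 4.6.1 and 6.3. Leave unchanged the two-subject count, the dose-level and relatedness conditions, the one-subject anaphylaxis trigger and the review by investigator and sponsor.

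The cost is two words in four places at the next amendment, with no new data or staff. The downside is that the review may occasionally be called when the present wording would not call it.

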5.4.8. Pharmacokinetic Dose Adjustment/Stopping Criteria

The exposures observed in animal toxicology studies will be used to guide dose escalation. Systemic exposures in the human subjects in this study may exceed the systemic NOAEL animal exposures from 4-week GLP toxicology studies as long as the doses administered in the study are safe and well tolerated.

For Part 1, the need to dose escalate will be evaluated if no meaningful increase in exposure is observed with an increase in dose (i.e., a plateau in exposures is reached).

5.5. Subject and Study Completion

A completed subject is one who has completed all phases of the study including the Follow-up visit.

The end of the study is defined as the last subject's last visit.

6. STUDY TREATMENT

6.1. Investigational Product and Other Study Treatment

The term 'study treatment' is used throughout the protocol to describe any combination of products received by the subject as per the protocol design. Study treatment may therefore refer to the individual study treatments or the combination of those study treatments.

	Study Treatment	
Product name:	GSK3342830	Placebo
Formulation description:	A lyophilized formulation aseptically manufactured as a pyrogen-free, white to yellowish brown powder containing 1000 mg of GSK3342830A (as free base) per vial	A clear and colorless solution containing 0.9% sodium chloride
Dosage form:	Lyophile	IV solution
Unit dose strengths/Dosage levels:	Unit dose strength: 1000 mg/vial as free base equivalent Dosage levels: Part 1: 250, 500, 1000, 2000, 4000, and ≤6000 mg Part 2: 1000, 2000, and ≤4000 mg Part 3: 250, 500, 1000, 2000, 4000, or ≤6000 mg	Not applicable
Route of Administration:	IV infusion over 1 hour	IV infusion over 1 hour

	Study Treatment	
Product name:	GSK3342830	Placebo
Dosing instructions:	
Parts 1 and 3: Single IV infusion.
 
Part 2: Single IV infusion on Day 1, TID IV infusions (approximately every 8 hours) on Days 2, 3, 4, 5, 6, 7, 8, 9, 10, 11, 12, 13, and 14, and a single IV infusion on Day 15.
 
Instructions for the preparation of the IV drug are included in the Pharmacy Manual.
	
Parts 1 and 3: Single IV infusion.
 
Part 2: Single IV infusion on Day 1, TID IV infusions (approximately every 8 hours) on Days 2, 3, 4, 5, 6, 7, 8, 9, 10, 11, 12, 13, and 14, and a single IV infusion on Day 15.
 
Instructions for the preparation of the IV drug are included in the Pharmacy Manual.

Physical description:	
The lyophilized powder cake has a white to yellowish brown color.
 
The reconstituted solution is a clear, colorless to yellow or brownish yellow liquid, free from visible particulate matter.
	A clear colorless solution

6.2. Treatment Assignment

Eligible subjects will be assigned to study treatment in accordance with the randomization schedule generated by PPD, before the start of the study, using validated internal software. Within each cohort, subjects will be randomly assigned to receive either GSK3342830 or placebo in a ratio of 3:1 in Part 1 and 4:1 in Part 2.

[figure not shown]
Each subject scheduled to receive study treatment will receive a treatment allocation number when randomized. The treatment number will indicate if the subject is to receive the scheduled dose of GSK3342830 or placebo.

6.3. Planned Dose Adjustments

- This protocol allows some alteration from the currently outlined dosing schedule. The maximum daily dose is planned to not exceed 6000 mg in Parts 1 and 3, and 4000 mg in Part 2.
- The decision to proceed to the next dose level of GSK3342830 will be made by the GSK study team and the investigator based on preliminary safety, tolerability, and PK data obtained in approximately 4 subjects for Part 1 and approximately 5 subjects for Part 2 that received active study treatment in the prior dose level. The actual doses to be administered may be adjusted based on the preliminary safety, tolerability, and PK data at previous dose levels; these dose adjustments may involve either an increase or a decrease in the planned dose. A schematic of the planned study design is presented in [Figure 3](#).

- The dosing schedule may also be adjusted to expand a dosing cohort to further evaluate safety and PK findings at a given dose level, or to add cohorts to evaluate additional dose levels. The study procedures for these additional subject(s) or cohort(s) will be the same as those described for other study subjects.
- If AEs, which are of severe intensity or greater and are consistent across subjects in a given dose level, or if unacceptable pharmacological effects, reasonably attributable in the opinion of the investigator to dosing with GSK3342830, are observed in 2 or more subjects in a dose level, further dose escalation will be temporarily halted and no further subject in subsequent cohorts will be dosed until a full safety review of the study has taken place. Relevant reporting and discussion with the medical monitor, relevant GSK personnel, and with the Ethics Committee will then take place before any resumption of dosing.
- If the same SAE occurs in more than 1 subject, further dose escalation will be temporarily halted and no further subject in subsequent cohorts will be dosed until a full safety review of the data has taken place.
- The previously mentioned criteria will apply even if measured PK parameters are below the PK stopping criteria, and every effort will be made to take a blood sample at the time of the event for PK analysis in the presence of any of the above events.

Figure 3 Planned Study Schematic

